#### 3.3 Exclusion Criteria

- ✓ Use of IVIG 7 days prior to planned IdeS® administration
- ✓ Recipients of Extended Criteria Donors (ECD) or Living Donors (LD)
- ✓ Lactating or pregnant females.
- ✓ Women of child-bearing age who are not willing or able to practice FDA-approved forms of contraception.
- ✓ HIV-positive subjects.
- ✓ Subjects who test positive for HBV and HCV DNA and/or RNA PCRs.

[figure not shown]
- ✓ Subjects with active TB.
- ✓ Subjects with selective IgA deficiency, those who have known anti-IgA antibodies, and those with a history of anaphylaxis or severe systemic responses to any part of the clinical trial material.
- ✓ Subjects who have received or for whom multiple organ transplants are planned.
- ✓ Recent recipients of any licensed or investigational live attenuated vaccine(s) within two months of the screening visit (including but not limited to any of the following:
  - Adenovirus [Adenovirus vaccine live oral type 7]
  - Varicella [Varivax]
  - Hepatitis A [VAQTA]
  - Rotavirus [Rotashield]
  - Yellow fever [Y-F-Vax]
  - Measles and mumps [Measles and mumps virus vaccine live]
  - Measles, mumps, and rubella vaccine [M-M-R-II]
  - Sabin oral polio vaccine
  - Rabies vaccines [IMOVAX Rabies I.D., RabAvert])
- ✓ A significantly abnormal general serum screening lab result defined as a WBC <  $3.0 \times 10^3/\text{ml}$ , a Hgb < 8.0 g/dL, a platelet count <  $100 \times 10^3/\text{ml}$ , , an SGOT > 3X upper limit .
- ✓ Individuals deemed unable to comply with the protocol.
- ✓ Subjects with active CMV or EBV infection as defined by CMV-specific serology (IgG or IgM) and confirmed by quantitative PCR with or without a compatible illness.
- ✓ Subjects with a known history of previous myocardial infarction within one year of screening.
- ✓ Subjects with a history of clinically significant thrombotic episodes, and subjects with active peripheral vascular disease.
- ✓ Subjects with Protein C and Protein S deficiency
- ✓ Use of investigational agents within 4 weeks of participation.
- ✓ Known allergy/sensitivity to IdeS® infusions

## 4 Study Design & Methods

Background: This is a single center, Phase I/II, open label exploratory study. The trial will primarily examine the safety and tolerability of IdeS® (Hansa Medical, Lund Sweden) given 4-6 hours prior to kidney transplantation to reduce or prevent complement-dependent, antibody-mediated rejection (ABMR) in 20 subjects (adult) who are highly-HLA sensitized (HS) as determined by the Calculated Panel Reactive Antibody Test (CPRA), have undergone desensitization with IVIG + rituximab and/or plasmapheresis and are awaiting LD/DD kidney transplant at Cedars-Sinai Medical Center. Patients will be screened for study eligibility once transplant offers are entertained. If the patient agrees to participate in the study, a donor-specific crossmatch will be performed to detect anti-HLA antibodies and donor-specific anti-HLA antibodies (DSA) which are associated with ABMR and/or graft loss. DSA will be detected using solid phase assay systems currently utilized at the Cedars-Sinai Medical Center HLA Laboratory ([name], Director, [contact]). These anti-HLA antibodies may result naturally or from previous pregnancy, transfusions, or prior transplants. If acceptable crossmatches and DSA levels are seen after desensitization, twenty patients will proceed to DD transplantation as previously described. Patients receiving

transplants will have pre-transplant labs for screen ADA, DSAs, FCMX, C3 and C4 obtained as outlined (See Study Protocol in Appendix A). In addition to the standard post-transplant immunosuppressive protocol, all patients will receive 0.24mg/kg IdeS® on day 0 on call to the OR prior to transplant procedure. Pre-medications will be given to patients as a precaution with Solumedrol 40mg IVP, Tylenol 650mg PO and Benadryl 50mg PO to minimize the risk of infusion reactions. Crossmatch and DSA tests will also be assessed on day 1 post-transplant to determine the effect of IdeS®. A protocol biopsy will be performed at 6M to assess the allograft for evidence of ABMR, including C4d staining using Banff 2013 criteria. Since ~25% of HS patients experience ABMR post-transplant and 80% of these ABMR episodes occur in the 1st post-transplant month, we feel the assessment of the potential impact of IdeS® therapy is best assessed in this time period. Patients who have evidence of allograft dysfunction will have non-protocol biopsies for cause. After completion of the IdeS® therapy, patients will be followed up to 6M to assess allograft function and ABMR episodes as well as DSAs. A protocol biopsy will be performed at 6M. The protocol is summarized in Fig. 12.

Figure 12

The entered subjects will be followed to determine if the use of IdeS® for prevention of ABMR in this high risk transplant population is safe and without infectious risks. In addition, we will determine the proportion of who developed evidence of ABMR within 6M of completion of the study. We will assess the transplanted patients to determine the number who sustain a viable and functioning kidney allograft for 6 months. All subjects will be evaluated on an intent-to-treat basis. The subject accrual rate will be limited to no more than five subjects per month in the initial three months to assure safety to all subjects. Repeat laboratories will be performed at the completion of IdeS® therapy to determine effect on levels and correlation with any potential events. A detailed analysis of the study is discussed below.

## 4.1 Study Analysis

This single-center, Phase I/II, trial is designed to examine the safety, tolerability and limited efficacy of human IdeS® (0.24mg/kg) given as per protocol (Appendix A) in 20 subjects (adults only) who are highly-HLA sensitized and are awaiting DD kidney transplant. Patients considered for this study will be desensitized using high-dose IVIG + rituximab and/or plasmapheresis. Patients who have received IVIG within 7 days from transplant offer will be excluded from study in order to minimize interactions with IdeS® infusion and circulation of IgG from IVIG infusion. Once transplant offers are entertained, a donor-specific crossmatch will be performed to detect anti-HLA antibodies which are associated with risk for ABMR. The specifics of our patient selection for desensitization, desensitization protocol, CMX testing and post-transplant protocols are outlined below:

## 4.2 Defining the Sensitized Patient

For the purposes of this study, we define HLA sensitization as a patient awaiting kidney transplantation on the UNOS waitlist who has a CPRA of  $\geq 50\%$  who also has demonstrable DSA using luminex bead technology and a history of sensitizing events (previous transplants, blood transfusions and/or pregnancies). These individuals must also have sufficient wait time on the UNOS list to allow for frequent offers with a history of positive crossmatches (DD) or an incompatible (LD) with a positive flow cytometry (FCMX), complement-dependent cytotoxicity (CDC+) crossmatch.

## 4.3 Defining ABMR

For purposes of this investigation, antibody-mediated rejection (ABMR) is defined as follows:

- ✓ Deterioration of allograft function in a high-risk transplant recipient (i.e. sensitized patient with history of DSAs) measured by serum Cr and eGFR (defined as a decline  $>20\%$  from baseline).
- ✓ Association with the presence of DSA (usually increasing in strength) measured by luminex techniques.
- ✓ Biopsy evidence of capillaritis, inflammation and C4d deposition.

Figure 13 below shows the course of a highly-sensitized (HS) patient who developed ABMR after receiving desensitization for incompatible kidney transplantation. Note,

DSAs increase with evidence of allograft dysfunction. This is associated with significant biopsy findings including evidence of complement activation and inflammation.

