## 1.2. Therapeutic Use of IdeS® for Prevention of Antibody- Mediated Injury

As mentioned above, alloantibodies are a major deterrent to access to and success of life-saving organ transplants. Despite advancements in desensitization, designing efficient and effective means of removal of pathogenic HLA antibodies remains a significant medical challenge. Preliminary data suggests that IdeS® exhibits fast and efficient enzymatic digestion of pathogenic antibodies in animal models of autoimmunity and on human autoantibodies. Data from patients with autoimmune neuromyelitis optica (NMO) shows that the complement activating and ADCC activity of the autoantibody, anti-aquaporin-4, is completely inhibited *in vitro* by IdeS® treatment. In addition, *in vitro* treatment of DSA positive serum from highly-HLA sensitized patients awaiting transplantation show complete inhibition of DSA activity in the solid phase luminex assay (see example in figure 1). The collective data from 12 highly sensitized patients demonstrated that IdeS treatment significantly reduced the reactivity in all tested patient sera to individual MHC class I and II antigens, as well as the reactivity in complement dependent cytotoxicity tests.

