## 2.2.4 Pharmacodynamics (PD)

SDS-PAGE analysis revealed that complete conversion of the IgG pool into single cleaved IgG (sIgG) was observed in three out of eight subjects dosed with 0.01 mg/kg BW IdeS. SclgG represents partially cleaved IgG where one of the two IgG heavy chains is cut by IdeS. A minor fraction of sclgG was further converted into F(ab')2- and Fc-fragments in these subjects and a weak reduction in plasma IgG was seen. At the next dose level, 0.04 mg/kg BW, the SDS-PAGE analysis showed partial effect in one subject, intermediate effect in one subject and close to full effect in one subject.

[figure not shown]
The SDS-PAGE analysis of subjects dosed with 0.12 mg/kg BW of IdeS revealed that full or close to full effect was accomplished within 24 hours in all four subjects, i.e. IgG was fully cleaved into F(ab')2- and Fc-fragments (figure 8A and 8B). Furthermore, maximum conversion into F(ab')2- and Fc-fragments was reached six hours after dosing and this was confirmed using the PD-assay which showed that the level of intact IgG (plus sclgG) reached minimum levels six hours after dosing (figure 8). The PD-assay is a validated quantitative sandwich-ELISA based on a Fab-specific capture and an Fc-specific detector that measure intact IgG and sclgG, but not the F(ab')2/Fc-fragments generated through IdeS cleavage.

In subjects dosed with 0.24 mg/kg BW of IdeS the IgG pool was converted into sclgG already during dosing and maximal effect was accomplished 2-6 hours after dosing in all four subjects (see SDS-PAGE in figure 8A and B). Thus, IgG cleavage was more rapid at the highest dose level (i.e. 0.24 mg/kg BW), compared to the lower dose (i.e. 0.12 mg/kg BW). The rapid cleavage of human IgG into F(ab')2 and Fc seen with SDS-PAGE analyses was confirmed with the PD-assay which showed that 2-6 hours after dosing low plateau level was reached at less than 5% remaining IgG and it was concluded that this signal mainly originated from sclgG (figure 8). Newly synthesized intact IgG was again detectable in serum two weeks after dosing in all subjects and after three weeks the level of intact IgG had further increased and constituted the main IgG fraction in serum (figure 9). See figure 10 for a summary of the SDS-PAGE analysis results.

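### Luminex DSA is an element of the ABMR definition, but IdeS suppresses it early and no test is scheduled between Day 1 and Day 30, so early episodes may go uncounted

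*Combined protocol and SAP*

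**What the plan says.** Section 4.3 lists three elements of ABMR: a decline in graft function of more than 20% from baseline, "Association with the presence of DSA (usually increasing in strength) measured by luminex techniques", and "Biopsy evidence of capillaritis, inflammation and C4d deposition". It does not say that all three are needed, give a minimum number, or say when DSA must be measured relative to the biopsy. Section 4 applies a second standard to the 6-month protocol biopsy, "including C4d staining using Banff 2013 criteria", and does not relate it to 4.3.

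On the drug's effect on the marker, Section 1.2 reports that sera from sensitized patients treated in vitro "show complete inhibition of DSA activity in the solid phase luminex assay". Section 2.2.4 reports that in healthy subjects given 0.24 mg/kg, the dose used in this trial, a "low plateau level was reached at less than 5% remaining IgG" 2-6 hours after dosing. It adds that "Newly synthesized intact IgG was again detectable in serum two weeks after dosing in all subjects", and that intact IgG was the main fraction at three weeks.

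On sampling, Appendix A places DSA tests at Day 0, 6 hours, Day 1, Day 30, Day 90 and Day 180. Section 4 provides for-cause biopsies when graft function worsens but ties no DSA sample to them.

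On use of the rate, Section 3.1 aims to bring ABMR from about 25% to below 5%. Section 4 says that 80% of episodes occur in the first month and that the effect is best assessed then. It describes the outcome as "the proportion of who developed evidence of ABMR within 6M of completion of the study".

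**The concern.** The outcome definition contains the laboratory marker that the treatment is designed to remove. If the three elements are joint and DSA must be concurrent, a patient with falling function, capillaritis and C4d in the first weeks may not be counted. There are two routes to this: DSA may read negative because of the drug, or there may be no DSA result at all, since nothing is scheduled between Day 1 and Day 30. The plan has no rule for either case.

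This falls in the month that the protocol treats as most informative, and the result will be compared with a rate of about 25% from patients who did not receive IdeS (the Section 4.4 series was desensitized in 2006-2009; the first human study of IdeS began in 2013). A lower recorded rate could then reflect part graft protection and part failure to meet the serologic element, and the planned data summary could not separate the two.

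**Working it through.** **Inputs**
- Reference ABMR rate: about 25% (Sections 3.1 and 4).
- Timing A: 80% of episodes in month 1 (Section 4).
- Timing B: 7 of 19 episodes by day 42, median day 109 (Section 4.4).
- Sample size: 20, single arm (Section 4.1).
- Masked period: days 0-14. This is an assumption, taken from the two-week point in Section 2.2.4.
- Further assumptions: no true drug effect, every episode in the masked period fails the DSA element, and episodes are evenly spread within each quoted period.

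**Step 1. Reproduce the plan's own rate.** 19/80 = 23.75%, which rounds to the stated 24%. The denominator is the 80 patients transplanted; 19/108 would be 17.6%.

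**Step 2. Compare the two statements on timing.** 7/19 = 37% by day 42 does not agree with 80% in month 1. The documents do not resolve this, so both are carried forward.

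**Step 3. Share of episodes in days 0-14.**
- Timing A: 0.80 × 14/30 = 0.373.
- Timing B: (7/19) × 14/42 = 0.123.

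**Step 4. Recorded rate = 0.25 × (1 − share).**
- No masking: 25.0%, or 5.0 of 20 expected.
- Timing B: 0.25 × 0.877 = 21.9%, or 4.4 of 20.
- Timing A: 0.25 × 0.627 = 15.7%, or 3.1 of 20.

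The expected loss is therefore 0.6 to 1.9 patients of 20.

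**Step 5. Chance of at most 1 case in 20** (1/20 = 5%, the edge of the target), from (1 − p)^20 + 20p(1 − p)^19:

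| Case | p | P(0) | P(0 or 1) |
|---|---|---|---|
| No masking | 0.250 | 0.3% | 2.4% |
| Timing B | 0.219 | 0.7% | 4.7% |
| Timing A | 0.157 | 3.3% | 15.6% |

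**Step 6. Sensitivity to full masking.** If only half of the episodes in days 0-14 were masked, Timing A gives 0.25 × (1 − 0.5 × 0.373) = 20.3%, or 4.1 of 20.

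**Step 7. Is a DSA result available?** Between Day 1 and Day 30 the schedule offers none. In that interval the serologic element depends on unscheduled testing that the plan does not describe.

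**The case against.** Several points on the other side stand, and they limit what can be claimed.

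- A reader might infer that early rejections cannot meet the definition. Section 4.3 does not say that all elements are required or that DSA must be concurrent. Its functional element refers to a history of DSA, and every patient is DSA and crossmatch positive at entry (Section 3.2). The joint reading is the natural one, but it is not written.
- A reader might infer that IdeS blanks luminex DSA for two or three weeks. The complete inhibition is in vitro, and across 12 patients Section 1.2 says only that "IdeS treatment significantly reduced the reactivity in all tested patient sera". The time course is total IgG in healthy men, not luminex DSA in sensitized patients. Intact IgG was already detectable at two weeks in all of them, so a three-week mask is not supported and two weeks is nearer an upper limit. Section 4.3 itself anticipates DSA rebound.
- A reader might infer that the rate is biased downward. Section 1.1 says that cleavage stops complement-mediated and cellular injury, so absent DSA may be the true drug effect. Bias arises only if antibody-mediated injury occurs while DSA reads negative or is unmeasured.
- Masked episodes would not vanish from the report. Section 3 also lists the incidence of rejection and biopsy pathology, and Section 3.1 names C4d deposition.
- ABMR is a secondary outcome, and Section 7 says that the study is not powered for efficacy. No decision rule uses the probabilities above. Even 1 of 20 has an exact 95% interval of 0.1% to 24.9%.
- Section 4.4 does not say how ABMR was diagnosed in the historical series, so it cannot be shown that the two rates rest on different definitions.

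None of this supplies the missing rule. If absent DSA means absent injury, biopsies will tend to be negative and a second count will add few or no cases. The rule matters only where function and biopsy both point to ABMR.

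**Conclusion.** The concern holds as a risk of understatement that comes from an incomplete endpoint definition. Under the stated assumptions, a true 25% would be recorded as about 22% to 16%, and the chance of at most 1 case in 20 would rise from 2.4% to between 4.7% and 16%. These figures rest on full masking in days 0-14, even spread of episodes and no drug effect. Partial masking gives smaller losses.

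A reader might go further and suppose that masking alone could produce the target of under 5%. That would need all of the 80% of first-month episodes to fall by day 14 (0.25 × 0.20 = 5.0%). Nothing in the documents supports such clustering, and the centre's own series, with a median of day 109, points the other way.

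The consequence is confined to a secondary, unpowered outcome. It should still be settled before events are counted, because it determines what the ABMR rate can support.

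**What to change.** For endpoint counting only, with no change to patient management:

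1. State in Section 4.3 whether all three elements are required, and how this relates to the Banff 2013 reference in Section 4.
2. For biopsies up to a fixed Day 30, report two ABMR counts side by side. One requires concurrent luminex DSA where measured. In the other, the pre-dose Day 0 DSA satisfies the DSA element. Because all patients are DSA positive at entry, the second is in effect function plus biopsy, so it should stand beside the concurrent-DSA count and not replace it.
3. Label an episode with no concurrent DSA result as missing, not negative.
4. Do not claim a reduction in ABMR if it appears only in the concurrent-DSA count.
5. Count events from transplant to Day 180 in place of "the proportion of who developed evidence of ABMR within 6M of completion of the study", because Appendix A has no visit after Day 180.

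The Day 30 limit should be fixed and not tied to the return of intact IgG. The IVIG given at 7 days post-transplant (Section 4.5) supplies intact IgG unrelated to DSA, and PD sampling in Appendix A skips Day 14.

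The cost is about a paragraph of endpoint wording and one extra line in the results. No new scheduled test is needed, since the concurrent count uses DSA only where it was measured. The downside is that the second count may be less favourable and may include some injury that is not antibody-mediated.

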**Figure 13**

[figure not shown]

Figure 13 shows the course of DSAs after transplantation in this HS patient who received desensitization with IVIG + rituximab prior to transplant. Three DSAs were present at transplant (two moderate strength and one low strength) as determined by a Relative Intensity Scale (RIS) where 0 points is given for a negative DSA, 2 for low strength (1000-2000 MFI), 5 for moderate (2000-5000 MFI) and 10 for high (>5000 MFI). The course of SCr, DSAs and biopsy are shown as well as responses to treatment with IVIG + rituximab.

The presence of DSAs has a strong correlation with C4d deposition and biopsy evidence of ABMR. Thus, this study will assess the ability of IdeS® to alter or prevent ABMR in DSA + patients. Important observations will be the assessment of efficacy of IdeS® in enzymatic cleavage of DSAs, the duration of this effect and the potential for rebound DSA responses after this unique therapy. We will also assess development of anti-IdeS® antibodies and determine if these responses are altered by desensitization.

#### 4.3.1 Treatment of Antibody Mediated Rejection (ABMR)

Biopsy-proven rejection episodes are treated with “pulse” methylprednisolone (10mg/kg/day, max 1000mg for >100kg for 3 days) and anti-thymocyte globulin (1.5mg/kg daily X 4) for cell-mediated rejection episodes that are unresponsive to pulse steroids. For patients experiencing ABMR, patients will initially receive pulse methylprednisolone (10mg/kg/day, max 1000mg for >100kg) IV daily x 3 doses then, depending on severity, IVIG 10% solution 2gm/kg (max 140g for >70kg) IV X1 dose followed by rituximab (375mg/m^2) IV X1 dose. In cases where rapid deterioration of allograft function is seen and/or thrombotic microangiopathy is seen on biopsy, the patient will receive plasma exchange X3-5 sessions followed by anti-C5 (Eculizumab®) IV weekly X4 weeks (1200mg week #1 followed by 900mg/ weekly for 3 additional

[figure not shown]
weeks). Efficacy of therapy will be assessed by determining renal functional improvement, monitoring DSA responses and repeat allograft biopsies, if needed.

#### 4.4 IVIG/Rituximab Desensitization Protocol

All HS who meet criteria for desensitization will receive IVIG 10% solution (2.0 g/kg [maximum 140 g per dose] on days 1 and 30) and rituximab (1 g administered on day 15). When a DD kidney offer becomes available, a donor-specific FCMX is performed pre-transplant. An acceptable CMX is defined as a negative complement-dependent cytotoxicity (CDC), at least at a 1:2 dilution of sera. A positive T-and B-cell FCMX with a shift of less than 225 channel shifts (CS) is also acceptable (negative: <100 mean channel shifts [MCS] for B cell and <50 MCS for T cell). Solid-phase antibody analysis was also used to define the specificity of the antibodies detected, to follow the effect of desensitization, and the strength of DSA as reported previously. Since the B-cell cytotoxicity and FCMX crossmatches are falsely elevated by rituximab, a heavier reliance on T-cell FCMX data and DSA values (<100,000 standard fluorescence intensity [SFI] units) is used as the primary determinants of CMX acceptability as described previously and illustrated below.

[figure not shown]
An analysis of the effects of the IVIG + rituximab desensitization protocol on DSA levels is shown in Figure 14A. Figure 14B shows the relationship of DSA levels and FCMX results. The data confirm that a cutoff of ~225 channel shifts (CS) for FCMX and DSAs <100,000 SFI units is associated with lower risk for ABMR compared with higher DSA levels and FCMX >225 CS.

